3.9. Data Analysis

The quantitative data analysis will be led by the study statistician, [name]. [name] has agreed access to the NHS Education for Scotland network for data analysis. Restricted access to the data will be provided to [name] for the purpose of analysis by making the data available on a restricted area of the secure network. All analysis will be carried out on NHS Education for Scotland computers.

A single principal analysis will be conducted post-randomisation following an intention-to-treat framework. The analysis will estimate the difference between the average proportion of patients contacting a healthcare professional between the two randomised groups. We will use a cluster-level analysis with weighted linear regression¹⁹ to estimate the treatment effect of the intervention with 95% confidence intervals. We will adjust the analysis for appropriate covariates.

Qualitative analysis will be led by [name]. Qualitative data from any free-text boxes in the questionnaire, and the online interviews will be analysed using thematic analysis, whereby data is coded into themes that emerge from commonalities or repeated patterns in the data²⁰. This will be undertaken following the six-step process outlined in Braun and Clarke (2006): familiarisation with the data; assigning preliminary codes; searching for patterns in codes; reviewing themes; defining and naming themes; production of final report.

4. Follow-up

There is potential for a longer-term follow-up of participating patients by looking at routinely collected data held by Public Health Scotland (ICD10 database) to determine the diagnostic accuracy of the Diabetes UK Risk Assessment tool when implemented in a dental setting. Participating patients will be asked in the consent form if they agree to be contacted about this follow-up up to 2 years following the study. Not providing consent for this aspect would not preclude patients from taking part in the main study.

5. Data Handling and Storage

5.1. Data Handling and Access

Participating dental practices will be required to identify, recruit and consent patient participants using their patient records. The study team will not have access to patient records. Study paperwork (eligibility checklist, consent form, case report form) will be online with the responses coming directly to the study team. Participating dentists will be responsible for ensuring the appropriate paperwork is completed for each patient. If a paper copy of the consent form is requested by the patient, then these will be stored securely within the dental practice and transferred to the study team on a weekly basis. No personal data collected for the study will be retained by the participating practices.

Participating dentists and dental practices will not be responsible for collecting data from the questionnaires and interviews; this will be the responsibility of the study team. The study team will contact participants about the questionnaire and interview via their preferred method of communication (given in the consent form). Paper copies of the questionnaire may be requested by participants; if so, these will be sent via post. Once completed questionnaires are returned to the study office, the responses will be entered online by a study administrator; the paper copy will be scanned, saved online, and then destroyed.

Members of the study team will have access to personal data only when required. Participating dentists and dental practices will only have access to data from their own practice. When contact is required with participants from the study team in order to contact participants with the link to the questionnaire and recruit for interviews, a limited number of people from the study team (e.g. chief investigator, administrative support) will have controlled access to personal data to allow emails/letters to be sent.

All data collected during the course of the study will be pseudonymised after data collection but before data analysis. Participants will be allocated a participant number by the study team, which will be linked to their name and email address (or other preferred method of communication, e.g. postal address or telephone number); this information will be kept in a password-protected link file and kept separate from the data.

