3.3. Sample, Recruitment and Eligibility

All dentists (principal, associate, VDP) working in vocational training practices in Scotland will be contacted via existing vocational training networks inviting them to take part. Eligibility criteria is shown in Table 1.

Participant	Inclusion	Exclusion	
Group			
Practices	vocational training practiceBased in Scotland	Not a vocational training practiceOutside of Scotland	
Practitioners	 Dentist working in a vocational training practice in NHS General Dental Service VDP Principal dentist Associate dentist Private dentists 	 Practitioners in: Public Dental Service Hospital Dental Service 	
Patients	 Adults ≥ 40 years Attending a vocational training practice for a non-emergency appointment English speaking 	 Adults < 40 years Patients attending for emergency treatment Patients who are pregnant Patients who have been previously diagnosed with diabetes or non-diabetic hyperglycaemia Patients who do not speak English 	

Table 1: Eligibility criteria for all participant groups

Patients will be recruited via communication from their dental practices. Patients will be contacted about the study when they receive their standard appointment reminder message. This can be via email or the patient's preferred method of communication. This recruitment message will contain information about the project and the participant information sheet will also be provided. Patients will be advised that if they wish to take part in the project they should bring their height, weight and waist measurements with them to their next appointment. At the appointment they will be assessed for their eligibility, given the opportunity to ask questions about the study, and asked to consent to their participation.

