3.4. Randomisation

All eligible NHS dental training practices in Scotland will be invited to take part (n=140). Eligible practices agreeing to take part will be randomised to either signpost or directly refer patients to their GP if their risk assessment score was "moderate" or "high". An automated system will randomise eligible practices on a 1:1 basis. A computer-generated stratification programme, incorporating a random element, will ensure intervention arms are balanced for practice size.

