3.5. Intervention groups

There will be 2 intervention groups. Practices in Group 1 will signpost their patients to a healthcare professional. Practices in Group 2 will directly refer their patients to a healthcare professional (see Figure 1).

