3.8. Data Collection

Once a patient has been confirmed as being eligible to participate, and has consented, the dentist will then complete the risk assessment online tool with the patient. The patient will be informed before

attending the appointment what information they will need, and will be asked to take their own measurements (weight, height, waist circumference) before attending. They will be provided with information beforehand about how to take these measurements. Participating dentists will be required to keep a record of the number of patients they conduct the risk assessment with, and the outcome of that assessment, i.e. the patient's risk assessment score, and what action was taken. This information will be stored in the Case Report Form.

Both signposting and referral will involve standardised resources, developed by VDPs. Dentists who signpost patients will be provided with an information leaflet with key information for patients. Dentists who make a direct referral to their patients' GP practice or pharmacist will be provided with a standardised referral letter template. This letter can be customised with patient details and then hand delivered or emailed to the patient's GP practice or pharmacist.

An online self-report survey will be sent to all patients one month following their risk assessment. Paper copies will be available for participants who have not supplied an email address, or who do not have internet access. For patients who were at moderate or high risk, they will be asked if they have contacted a healthcare professional about the outcome of their risk assessment. Due to the impact of COVID-19 restrictions, attendance at a GP practice in person may not be possible; as such, we will consider any verbal contact with GP or other healthcare professional, either in person or via telephone, as "contact" for the purposes of this study. This survey will also measure the secondary outcomes for all patients, i.e. their beliefs and experiences about receiving a general health check. Patients will be asked about their thoughts on the acceptability of general health checks in a dental setting, how they felt about being told their risk score and how they felt about being referred/signposted if they were at moderate or high risk. Demographic information will also be collected. A flow diagram of the patient journey is presented in Figure 2.

Figure 2: Patient Journey

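### Practices that will know their arm recruit the patients, with no all-eligible or consecutive rule and no count of those invited, so recruitment could differ by arm and be only partly visible

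*Protocol*

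**What the plan says.** Protocol section 3.4 allocates whole practices: "Eligible practices agreeing to take part will be randomised to either signpost or directly refer patients to their GP". It adds: "An automated system will randomise eligible practices on a 1:1 basis". The stratification "will ensure intervention arms are balanced for practice size"; no patient characteristic is mentioned. Section 3.5 gives each practice a single strategy, for example: "Practices in Group 1 will signpost their patients to a healthcare professional". Under section 3.8 the signposting arm uses an information leaflet, and the referral arm uses a template letter that is customised and sent on.

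Patients come in after that. Section 5.1 says: "Participating dental practices will be required to identify, recruit and consent patient participants using their patient records". Section 3.3 gives the route: "Patients will be contacted about the study when they receive their standard appointment reminder message". Eligibility, questions and consent are dealt with at the appointment. Section 3.7 asks each dentist for 20 patients.

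On records, section 3.8 says: "Participating dentists will be required to keep a record of the number of patients they conduct the risk assessment with", along with the score and the action taken. Section 5.1 lists an online eligibility checklist, consent form and case report form that go directly to the study team, and adds: "The study team will not have access to patient records".

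**The concern.** In a cluster trial, randomisation balances practices in expectation. It balances patients only if they are identified before allocation is known, or by a rule that leaves no room for choice. Neither holds here. Allocation comes first, the people who recruit are those who will deliver the allocated strategy, and the target of 20 has no rule for which 20.

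The work per at-risk patient also differs between arms: handing over a leaflet, or preparing and sending a letter. That is a plausible reason for recruitment to run differently, even without intent.

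The outcome is the proportion of patients who contact a healthcare professional, so it depends directly on how ready the enrolled patients are to act. If that readiness differs by arm because of who was enrolled, the difference enters the estimate as if it were an effect of referral. Without counts of patients invited and approached, a reader of the results could not judge how far this happened.

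**Working it through.** **Order of events.** Practice agrees, practice is randomised (3.4), practice delivers one strategy (3.5, 3.8), practice invites, checks eligibility and takes consent (3.3, 5.1), dentist completes the risk tool (3.8). No step identifies patients before allocation, and no recruiter unaware of the arm is described. That recruiters know their arm is inferred from this sequence; no sentence says so.

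**What would be visible.**
- Number assessed, risk score and action: recorded (3.8).
- Demographics: collected in the one-month survey (3.8).
- Patients seen but not enrolled: perhaps some, through the eligibility checklist (5.1).
- Patients invited, or eligible and never invited or approached: no count required.

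**The plan's own figure.** Inputs from 3.7: 70 practices per arm, SD of practice proportions 0.25, difference 0.12. Two-sided alpha of 0.05 is assumed, in line with the 95% confidence intervals in 3.9.
- SE of the arm difference = 0.25 × sqrt(2/70) = 0.0423, or 4.2 points.
- Power = Φ(0.12/0.0423 − 1.96) = Φ(0.88) = 81.1% (80.5% by noncentral t).

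This reproduces the stated 80%, which is not in dispute.

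**Illustration of bias (all patient-level inputs assumed; none is in the protocol).** Likely responders make contact at 80%, others at 30%.
- 50:50 mix: 0.5 × 0.80 + 0.5 × 0.30 = 0.55, the plan's assumed rate.
- 60:40 mix: 0.6 × 0.80 + 0.4 × 0.30 = 0.60.
- Spurious difference: 0.05, or 5/12 = 42% of the target difference.
- False-positive rate with no true effect: 0.05/0.0423 = 1.18; 1 − Φ(1.96 − 1.18) + Φ(−1.96 − 1.18) ≈ 0.22.

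**Range under other assumptions.** Bias = (gap in contact rate between patient types) × (difference between arms in the share of likely responders).

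| Gap | Share difference | Bias | False-positive rate, no true effect | Power for a true 12 points, bias opposed |
|---|---|---|---|---|
| 0.20 | 0.10 | 2 points | 7.6% | 65.8% |
| 0.30 | 0.20 | 6 points | 29.5% | 29.5% |
| 0.40 | 0.20 | 8 points | 47.3% | 15.5% |

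More practices would shrink the SE but leave the bias unchanged.

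**The case against.** The strongest reply is that section 3.3 describes a routine channel. The study message goes with the appointment reminder, and patients who wish to take part bring their measurements. That is largely self-selection by patients, and the sentence in 5.1 about patient records sits under data handling. A reader might infer that dentists hand-pick 20 patients from their files; the protocol does not describe that. What stands is that 3.3 does not say every eligible booked patient gets the message, and that eligibility and consent are handled in the practice.

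Three other stronger readings are tempting and are not supported:
- *The unblinded dentist forms the analysis set.* The risk category is calculated by a fixed online tool, largely from measurements that patients take themselves, and only after consent. At recruitment a dentist can only guess who will score moderate or high.
- *Patients are told different things in each arm.* The message and information sheet are not shown, so this cannot be tested.
- *Selection could not be detected at all.* Enrolment skewed towards lower-risk patients would show in the recorded scores. Selection on readiness to act would not.

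The planned covariate adjustment (3.9) can help for measured factors. Intention-to-treat preserves the allocation of practices but does not correct for which patients entered after it.

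**Conclusion.** The point holds as a cheap improvement. As written, the protocol lets practices that will know their arm recruit without an all-eligible or consecutive rule and without a count of those invited. Differential recruitment is possible. The documents do not show that it will occur, nor in which direction.

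An assumed 10-point difference in patient mix, with contact rates of 80% and 30%, gives a spurious 5 points and a false-positive rate of about 22%. Other assumed inputs give 2 to 8 points. These figures show sensitivity and are not estimates.

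A reader might push the illustration until the whole 12-point target is spurious. That needs a 74:26 mix, because (0.67 − 0.30)/0.50 = 0.74: a 24-point shift in one direction averaged over an arm of 70 practices. Nothing in the protocol supports such a shift. Nor does it follow that randomisation gives no protection, since practices remain balanced in expectation.

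**What to change.** In sections 3.3 and 3.8, state that from a fixed start date the study message goes with the reminder of every patient aged 40 or over who is booked for a non-emergency appointment, and that dentists approach consecutive eligible attenders until 20 are recruited. Have each practice report anonymous counts of patients invited, eligible and consented. In section 3.9, commit to comparing these counts, baseline characteristics and the moderate/high-risk share by arm.

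The cost is a short regular count by each practice and a protocol amendment. Version 4 is dated May 2022, within a planned study period of February to December 2022, so recruitment may have begun. The rule and the counts can still start from the amendment date, and results before and after that date can be shown separately.

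Concealing the practice's strategy from patients until the score is known would go further, but it changes consent material and is not clearly cheap. It is not needed for this point.

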5.2. Data Storage

A. Personal Data

Electronic personal data will be encrypted and all data will be securely stored on NHS Education for Scotland servers and will only be accessed by login and password of the nominated team members, in accordance with the NHS Education for Scotland Corporate Information Security Policy and the Information Governance Policy. If paper copies of documents containing personal data are collected, high-resolution scans will be taken of the documents, the original paper copies destroyed and the scanned documents securely stored on the NHS Education for Scotland servers as outlined above.

B. Research Data

Electronic copies of research data will be securely stored on NHS Education for Scotland servers. If the NHS Education for Scotland information governance regulations change during the study, this policy

will be reviewed and updated as appropriate. If paper copies of documents containing research data are collected, these will be scanned and the paper copies destroyed. The high-resolution scanned documents will be securely stored on NHS Education for Scotland as outlined above. Access to the data will be controlled by the data custodian ([name]) or a nominated delegate, and a Data Protection Impact Assessment will be completed before the study commences.

Interviews with participants will be audio and video recorded. These recordings will be destroyed at the end of the study.

5.3. Data Retention

Personal data will be retained for a period of two years following the end of the study, to allow the study team to follow-up patients who have consented to being contacted. If participants have not consented to being contacted, their personal data will be destroyed at the end of the study, once data analysis and write-up is complete. If a patient who has previously consented to being contacted in two years declines to participate in the follow-up study, their personal data will be destroyed. Research data will be stored for ten years following the end of the study.

6. Ethical Review and Governance

Ethical approval will be sought from an NHS Scotland Research Ethics Committee. Before any sites begin to recruit patients to participate, the Chief Investigator will ensure that appropriate approvals are in place. This work will be conducted in accordance with the UK Policy Framework for Health and Social Care Research and the 2018 edition of the Governance Arrangements for Research Ethics Committees. Any personal or special category data will be stored and managed in accordance with the General Data Protection Regulations (UK GDPR) 2018. A Data Protection Impact Assessment will be undertaken.

Informed consent will be obtained from all participants (patients and practitioners). Before consent is sought, all participants will be given the opportunity to read and ask questions about the participant information sheet. If any relevant new information becomes available during the course of the research then this will be conveyed to participants via their preferred method of communication from the study team.

7. Patient and Public Involvement

An experienced Patient and Public Involvement representative was involved in discussions about the initial development of the research project. Patient-facing resources have been developed with feedback from a small group of dental patients to ensure they are accessible and appropriate. Patient and public involvement will be sought towards the end of the project to help produce a plain English summary of results to be shared with patient participants.

8. Training

All participating practitioners will be required to complete Good Clinical Practice training before undertaking data collection. In addition, they will be asked to complete training provided by Diabetes UK for healthcare professionals and additional training will be offered by a member of the project advisory team regarding communicating with patients about diabetes.

9. Reporting and Dissemination

On completion of the study data will be analysed as outlined above, and a final study report will be prepared. This report will be made available and presented to the NHS Education for Scotland Dental Executive. A summary of findings will be made available to participants, and the VDPs who contributed to the study. The protocol and findings will also be submitted for publication in a peer-reviewed journal and presented at relevant conferences. In addition, other innovative methods of dissemination

will be explored, including online videos. Authorship of reports, papers or presentations will be determined by the criteria developed by the International Committee of Medical Journal Editors²¹.

10. Amendments

The Chief Investigator will be responsible for any amendments made to the protocol, and for communicating any substantive changes to the Research Ethics Committee and NHS R&D. Amendments will be noted in the "Amendment History" table below and the protocol version number will be updated accordingly.

Version Number	Date	Amendments	
Version 1	16/12/2021		
Version 2	05/02/2022	 Changes to the eligibility criteria to include requirement that patient participants must speak English. Sentence added to the "Ethical Review and Governance" section, to include that participants will be contacted if any relevant new information becomes available during the course of the research. New subsection added: 3.2 "Study setting" New section added "Data Handling and Storage". This becomes section 5; subsequent sections renumbered accordingly. Additional text added to Section 3.9. "Data Analysis" to indicate who will be responsible for analysis of quantitative and qualitative data. Additional text added to Section 8 "Training" regarding 	
Version 3	08/03/2022	additional training to be offered to participating dentists.	
VEISIONS	00/03/2022	 Additional text added in Section 3.8 Data Collection regarding paper copies of questionnaires being available for patients who do not have internet access. 	
